2.4. Statistical Analyses

The primary objective of this study is to determine the safety and tolerability of a single intravenous dose of GSK2831781 in healthy Japanese and Caucasian participants, and a single subcutaneous dose of GSK2831781 in healthy Caucasian participants. No formal hypotheses will be tested.

An estimation approach will be used to describe pharmacokinetics of GSK2831781, where point estimates and corresponding 90% confidence intervals will be constructed, unless otherwise stated.

3. PLANNED ANALYSES

3.1. Interim Analyses

An interim analysis for Part A will be performed once at least 8 participants in each stratum have completed their Day 8 visit, and at least 6 participants in each stratum have completed their Day 29 visit, where Safety, PK and PD data will be reviewed. The interim analysis will be utilised to determine if Japanese participants can be recruited into the Phase 2 study (204869) under the existing dosing strategy.

An Interim Data Review Committee (DRC) will be utilised in this study to review the interim analysis data. The DRC will be composed of a limited number of people, who may be members of the 207823 study team, including the statistician, a senior safety representative, lead physician and the pharmacokineticist. A DRC Charter will contain the details regarding the DRC, including membership, decision rules for the interim, and required data integrity and data quality control.

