9.1.2. Derived Pharmacokinetic Parameters

Pharmacokinetic parameters will be calculated by standard non-compartmental analysis according to current working practices and using the currently supported version of WinNonlin. All calculations of non-compartmental parameters will be based on actual sampling times.

Pharmacokinetic parameters listed will be determined from the plasma concentration-time data, as data permits. Additional parameters may be included as required.

Parameter	Parameter Description
AUC(0-t)	
 Area under the concentration-time curve from time zero to the time of last quantifiable concentration (C(t)). Calculated using the linear trapezoidal rule for each incremental trapezoid and the log trapezoidal rule for each decremental trapezoid.
C _{max}	
 Maximum observed concentration. Determined directly from the concentration-time data.
t _{max}	
 Time to reach C_{max}. Determined directly from the concentration-time data.

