15.12.7. Pharmacokinetic Tables**Part A**

Pharmacokinetic Tables (Part A)					
No.	Population	IDSL / Example Shell	Title	Programming Notes	Deliverable [Priority]
Pharmacokinetic Concentrations					
3.1.	PK	PK01	Part A: Summary of GSK2831781 Plasma Pharmacokinetic Concentration-Time Data	Include 95% Confidence Interval for the mean. By treatment and geographic ancestry. IA: only include data up to Day 29.	IA SAC
Pharmacokinetic Parameters					
3.2.	PK	PK03	Part A: Summary of Derived GSK2831781 Plasma Pharmacokinetic Parameters	Include 95% Confidence Interval for the mean. By treatment and geographic ancestry.	IA SAC
3.3.	PK	PK05	Part A: Summary of Log-Transformed Derived GSK2831781 Plasma Pharmacokinetic Parameters	By treatment and geographic ancestry.	IA SAC
Pharmacokinetic Statistical Analyses					
3.4.	PK	[Non-standard] PK_T1	Part A: Table of Ethnosensitivity Model Results		SAC

Part B

Pharmacokinetic Tables (Part B)					
No.	Population	IDSL / Example Shell	Title	Programming Notes	Deliverable [Priority]
Pharmacokinetic Concentrations					
3.5.	PK	PK01	Part B: Summary of GSK2831781 Plasma Pharmacokinetic Concentration-Time Data	Include 95% Confidence Interval for the mean. By treatment.	SAC
Pharmacokinetic Parameters					
3.6.	PK	PK03	Part B: Summary of Derived GSK2831781 Plasma Pharmacokinetic Parameters	Include 95% Confidence Interval for the mean. By treatment.	SAC
3.7.	PK	PK05	Part B: Summary of Log-Transformed Derived GSK2831781 Plasma Pharmacokinetic Parameters	By treatment.	SAC
Pharmacokinetic Statistical Analyses					
3.8.	PK	[Non-standard] PK_T1	Part B: Table of Bioavailability Model Results		SAC

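### At the Part A interim, AUC(0-t) is summarised by ancestry with no common end time, and the planned Japanese:Caucasian ratio with 90% CI is delivered only at the final analysis

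*SAP*

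**What the plan says.** **Purpose and trigger (SAP 3.1).** "The interim analysis will be utilised to determine if Japanese participants can be recruited into the Phase 2 study (204869"), under the existing dosing strategy. It opens once at least 8 participants per stratum have passed Day 8 and "at least 6 participants in each stratum have completed their Day 29 visit". No upper limit on follow-up is given. The decision rules are left to the Data Review Committee (DRC) Charter, which is not among the documents.

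**Definition (SAP 9.1.2).** AUC(0-t) runs "from time zero to the time of last quantifiable concentration". "All calculations of non-compartmental parameters will be based on actual sampling times". No AUC over a fixed interval is defined, although "Additional parameters may be included as required".

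**Displays (SAP 15.12.7 and 15.12.8).**
- Table 3.2, "Part A: Summary of Derived GSK2831781 Plasma Pharmacokinetic Parameters", and its log-transformed counterpart, Table 3.3, are produced at both the interim and the final analysis, by treatment and geographic ancestry.
- The note "IA: only include data up to Day 29" stands on Table 3.1 (concentrations) and on Figures 3.1 and 3.2. It does not stand on Tables 3.2 or 3.3.
- Table 3.4, "Part A: Table of Ethnosensitivity Model Results", is marked for the final analysis only. It holds the SAP 9.5.1 ANOVA: the ratio of geometric means with 90% CI for AUC(0-t) and Cmax.

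**The concern.** Part A exists to compare the two ancestries, and this interim informs whether Japanese participants enter study 204869. For AUC, the committee receives group summaries in which each participant's area stops at his own last sample. If the strata differ in how far their active participants have been followed, the comparison mixes exposure with length of follow-up. A Day 29 cut would shorten long profiles but could not lengthen short ones. The one display built to estimate the ancestry effect, with its uncertainty, is held back until after the decision it would inform. AUC is one of only two measures in the planned ethnosensitivity model.

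**Working it through.** **Inputs.** Allocation 6 active to 2 placebo per stratum, and a between-subject CV for AUC(0-t) of 24.2% at 5 mg/kg (Protocol 10.2.1). Trigger from SAP 3.1. The documents give no half-life. I assume mono-exponential decline with half-life h = 10 to 25 days, all samples quantifiable, and no true ancestry difference.

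**1. The plan's own precision figure.** Log-scale SD = √ln(1 + 0.242²) = 0.2386. One group of 6: exp(t(0.95, 5) × 0.2386/√6) − 1 = exp(2.015 × 0.0974) − 1 = 21.7%, as Protocol 10.2.1 states. For the ratio, 6 v 6: exp(t(0.95, 10) × 0.2386 × √(1/6 + 1/6)) = exp(1.812 × 0.2386 × 0.5774) = 1.284. Sampling error alone therefore gives 90% limits of about 0.78 to 1.28 times the estimate.

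**2. How many active profiles can be short.** 8 − 6 = 2 per stratum, so 0, 1 or 2 of the 6 active. If exactly two of the 8 are short, and this is unrelated to treatment, at least one is active with probability 1 − 1/28 = 27/28 and both are with probability 15/28.

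**3. Bias with short profiles in one stratum only.** AUC to Day d is proportional to F(d) = 1 − 2^(−(d−1)/h). With r = F(stop)/F(29), one short profile of 6 multiplies that stratum's geometric mean by r^(1/6), and two multiply it by r^(1/3). Example, h = 10: F(8) = 1 − 2^(−0.7) = 0.384, F(29) = 1 − 2^(−2.8) = 0.856, r = 0.449, r^(1/6) = 0.875.

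| Short profile ends | r (h = 10 to 25) | Apparent ratio, one of 6 short |
|---|---|---|
| Day 8 | 0.449 to 0.327 | 0.88 to 0.83 |
| Day 15 | 0.725 to 0.596 | 0.95 to 0.92 |
| Day 22 | 0.895 to 0.817 | 0.98 to 0.97 |

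Two of 6 ending at Day 8 give 0.77 to 0.69. These are Japanese:Caucasian ratios if the short profiles are in the Japanese stratum, and reciprocals if they are in the Caucasian stratum.

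**4. One short profile in each stratum.** The bias cancels only if both stop on the same day. Day 8 in one and Day 22 in the other gives (F(8)/F(22))^(1/6) = 0.89 to 0.86. When both stop on the same day, precision still suffers: pooled variance = 0.2386² + (2 × 5/6 × (ln r)²)/10. At Day 8 the pooled SD is 0.405 to 0.515, and the upper 90% half-width rises from 28% to 53-71%. At Day 15 it is 33-40%, and at Day 22 it is 29-30%.

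**5. Sensitivity to the decline model.** Adding an early distribution phase (assumed half-life 1 to 2 days, intercept 0.5 to 2 times the terminal one), one of 6 ending at Day 8 gives 0.92 to 0.84.

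**6. Why a replacement AUC needs a nominal end time.** Under the main model, the Day 8 visit window of ±1 day moves the AUC by 11-13% (for example F(7)/F(8) − 1 = −11.5% to −13.1%). The Day 29 window of ±2 days moves it by 2-5%.

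**The case against.** The strongest reply is that the link to the decision is unseen. The Charter's rules are not available, so the weight given to AUC is unknown. That stands as a limit.

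The committee also receives like-for-like data: concentrations at matched times (Table 3.1), profiles (Figures 3.1 and 3.2, where a short one would show) and Cmax. This stands too, but Cmax does not measure elimination, and seeing a short profile does not correct the summary in Tables 3.2 and 3.3.

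Holding the ratio for the final analysis can be defended. No hypotheses are tested, and SAP 9.5.1 runs the ANOVA only on well-defined profiles. Table 3.3 gives geometric means, 95% CI and %CVb (SAP 9.2), so an approximate ratio and interval can be worked out by hand. They would, however, rest on the same unequal windows. Population PK does not need equal follow-up, but its displays come as needed, with no interim delivery stated. The Day 112 interim in Protocol 10.5 is optional and is not in SAP 3.1.

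On size, Day 8 is the most extreme stop day, and one such profile stays inside the 0.78 sampling limit. That is fair for one profile. Two, which the trigger also permits, reach or pass that limit.

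Three stronger readings are tempting, and the documents do not support them:
- A reader might infer that the interim comparison will be biased. The trigger permits unequal follow-up but does not make it certain, and equal follow-up would remove the bias.
- A reader might infer that, because the Day 29 note is missing from Tables 3.2 and 3.3, interim AUCs would run well past Day 29 in one stratum. The note is on the other interim PK, LAG3+ and sLAG3 time-course displays. Its absence from tables with no time axis is weak evidence of a different cut.
- A reader might infer that one short profile in each stratum is harmless. Step 4 shows that this holds for bias only when both stop on the same day, and even then precision can suffer.

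**Conclusion.** The point holds and should be fixed; confidence is medium. As written, the plan can put before the committee an AUC comparison by ancestry that is confounded with follow-up, without the planned ratio and interval. That the plan allows this follows from its text. The size is illustrative, because it rests on the assumed half-life, the decline model and no true difference. A single early-ending active profile costs 12-17% at Day 8, 5-8% at Day 15 and 2-3% at Day 22. Two at Day 8 in one stratum cost 23-31%. Cmax and matched-time concentrations are sound, and the final analysis is not in question here.

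**What to change.** 1. State the Day 29 cut on interim Tables 3.2 and 3.3. At the interim, replace AUC(0-t) with AUC(0-Day 8) (0-168 h) for all active participants and AUC(0-Day 29) (0-672 h) for active participants who completed Day 29, alongside Cmax. Show the number of active participants behind each, by ancestry.
2. End each AUC at the nominal hour. Use log-linear interpolation when a sample falls after it, and otherwise log-linear extrapolation by no more than the visit window (1 day at Day 8, 2 days at Day 29).
3. Produce Table 3.4 at the interim as well, on these AUCs and Cmax, as a geometric mean ratio with 90% CI and no test. AUC(0-t) stays the final-analysis parameter.

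**Cost.** SAP wording, two added parameters, which SAP 9.1.2 already allows, and one extra interim table. No new samples are needed. The added table is group level, and Tables 3.2 and 3.3 already go to the interim by treatment and ancestry, so no individual allocation is newly exposed.

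**Limits.** AUC(0-Day 8) keeps 6 v 6 (half-width 28%) but says little about late elimination. AUC(0-Day 29) may rest on as few as 4 v 4, where exp(1.943 × 0.2386 × √(1/4 + 1/4)) = 1.388, a half-width of about 39%. With 5 v 5 it is 32%. These half-widths assume that the AUC(0-t) CV of 24.2% carries over to partial AUCs, which the documents do not show. The two AUCs should be read together.

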3.2. Final Analyses

The final planned primary analyses will be performed after the completion of the following sequential steps:

1. All participants have completed the study as defined in Section 5.4 of the protocol: the end of the study is defined as the date of the last visit (including follow-up) of the last participant in the study (Parts A and B).
2. All required database cleaning activities have been completed and final database release (DBR) and database freeze (DBF) have been declared by Data Management.
3. All criteria for unblinding the randomisation codes have been met.
4. Randomisation codes have been distributed according to RandAll NG procedures.

4. ANALYSIS POPULATIONS

Population	Description	Analyses Evaluated
Screened	All participants who were screened for eligibility.	
 Study Population (specific only)
Randomized	All participants who are randomised into the study and receive a randomisation number.	
 Study Population (specific only)
Safety	All Randomized participants who receive study intervention. Participants will be analysed according to the intervention they actually received.	
 Study Population Safety PD PK/PD
Pharmacokinetic (PK)	All Safety participants for whom a PK sample was obtained and analysed. Participants will be analysed according to the intervention they actually received.	
 PK

Refer to [Appendix 12](#): List of Data Displays which details the population used for each display.

Note that a participant is considered evaluable if they have been dosed and have safety and PK data up to Day 29 (Parts A and B).

4.1. Protocol Deviations

Important protocol deviations (including deviations related to study inclusion/exclusion criteria, conduct of the trial, participant management or participant assessment) will be summarised and listed.

Protocol deviations will be tracked by the study team throughout the conduct of the study in accordance with the Protocol Deviation Management Plan.

- Data will be reviewed prior to unblinding and freezing the database to ensure all important deviations are captured and categorised on the protocol deviations dataset.
- This dataset will be the basis for the summaries and listings of protocol deviations.

A separate listing of all inclusion/exclusion criteria deviations will also be provided. This output will be based on data as recorded on the inclusion/exclusion page of the eCRF.

5. CONSIDERATIONS FOR DATA ANALYSES AND DATA HANDLING CONVENTIONS

5.1. General

Parts A and B will be reported separately, with separate outputs generated for each, unless stated otherwise.

5.2. Study Treatment & Sub-group Display Descriptors

In the Tables, Listings and Figures (TLF), treatment should be presented with placebo first, then in order of increasing dose within each part.

Part A: Treatment Groups Descriptions			
Randall NG		Data Displays for Reporting	
Code	Description	Description	Order in TLF
A	450 mg GSK2831781 IV	450 mg GSK2831781 IV	2
P	Placebo IV	Placebo IV	1

Treatment comparisons will be displayed as follows using the descriptors as specified:

1. 450 mg GSK2831781 IV vs Placebo IV

A subset of Part A data displays will be presented with a combination of treatment groups and geographic ancestry stratification, as described in Section 5.4.

Part B: Treatment Groups Descriptions			
Randall NG		Data Displays for Reporting	
Code	Description	Description	Order in TLF
B1	150 mg GSK2831781 SC injection 1 active	150 mg GSK2831781 SC injection 1	2 (*)
B2	150 mg GSK2831781 SC injection 2 active	150 mg GSK2831781 SC injection 2	3 (*)
B3	150 mg GSK2831781 SC injection 3 active	150 mg GSK2831781 SC injection 3	4 (*)
C	450 mg GSK2831781 SC	450 mg GSK2831781 SC	5
Q	Placebo SC	Placebo SC	1

(*) Note that treatment groups B1, B2 and B3 will be combined into a single “150 mg GSK2831781 SC” group in most tables, figures and listings. Only a small subset of outputs, including listings of injection site reactions (Section 15.12 for details), will report B1, B2 and B3 as separate treatment groups.

Treatment comparisons will be displayed as follows using the descriptors as specified, where “150 mg GSK2831781 SC” includes treatment groups B1, B2 and B3:

1. 150 mg GSK2831781 SC vs Placebo SC
2. 450 mg GSK2831781 SC vs Placebo SC

5.3. Baseline Definitions

- The baseline value (in both Parts A and B) will be the latest pre-dose assessment with a non-missing value, including those from unscheduled visits.
- If time is not collected, Day 1 assessments are assumed to be taken prior to dosing and used as baseline.
- Replicate assessments at a timepoint will be averaged, and the mean value will be used.
- Unless otherwise stated, if baseline data is missing no derivation will be performed and baseline will be set to missing.

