| Review | | | | | | | | | | | | | | | | | | | | |

Footnotes:

1. All post dose time points are in reference to the start of infusion.
2. Assessments at these visits should be on the scheduled day however can be at any time in the day.
3. Early withdrawal assessments will be the same as Follow-Up
4. End of infusion assessment time window is +30 minutes for all assessments except for the PK sample which should be collected just before the end of the infusion.
5. ECG in triplicate at screening and single at all other time points.
6. Vital Signs to be taken every 30 minutes from start of infusion until completion of 2hr post dose monitoring period.
7. PK sample at end of infusion should be collected just before the end of the infusion.
8. The genetic sample is optional and can be taken any time after consent has been signed and the participant is randomized.

The timing and number of planned study assessments, including safety, pharmacokinetic, and pharmacodynamic assessments may be altered during the course of the study based on newly available data (e.g., to obtain data closer to the time of peak plasma concentrations) to ensure appropriate monitoring.

Any changes in the timing or addition of time points for any planned study assessments as the result of emerging pharmacokinetic/pharmacodynamic data from this study must be documented and approved by the relevant study team member and then archived in the sponsor and site study files but will not constitute a protocol amendment. The Competent Authority (CA) and ethics committee (EC) will be informed of any safety issues that constitute a substantial amendment and require alteration of the safety monitoring scheme or amendment of the informed consent form (ICF). The changes will be approved by the CA and the EC before implementation.

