| Vital Signs ⁶ | X | X | X | | X | X | X | X | X | X | X | X | X | X | X | X | X | X | X | X | X |
| Randomization | | X | | | | | | | | | | | | | | | | | | | |
| IMP Administration | | | | X ⁷ | | | | | | | | | | | | | | | | | |
| Resident in Unit | | <-----> | | | | | | | | | | | | | | | | | | | |
| Local tolerability at injection sites | | | X | | X ⁸ | X | | X | | X | | | | | | | | | | | |
| sLAG3 concentrations | | | X | | | X | X | X | X | X | X | X | X | X | X | X | X | X | X | X | X |
| PK | | | X | | | X | X | X | X | X | X | X | X | X | X | X | X | X | X | X | X |
| Immunogenicity | | | X | | | | | | | | | | | | X | | X | | X | X | |

| Procedure | Screening (up to 28 days before Dosing) | Day - 1 | Day 1 | | | Days 2-85 | | | | | | | | | | | | | | Follow Up/Early Withdrawal (112 Days post dose) ³ |
|-------------------------------------|---|---------|------------|----|------------------------|----------------|----------------|----------------|----------------|-----|-----|-----|-----|-----|-----|-----|-----|-----|-----|--|
| | | | Pre-Dose | 0h | Post Dose ¹ | 2 ² | 3 ² | 4 ² | 6 ² | 8 | 11 | 15 | 18 | 22 | 29 | 43 | 57 | 71 | 85 | |
| Window | | | -60 min | | | | | | | ±1d | ±2d | ±2d | ±2d | ±2d | ±2d | ±3d | ±3d | ±3d | ±3d | ±7d |
| LAG3 ⁺ Cell Depletion | | | X | | | X | | X | | X | | X | | | X | X | X | | X | X |
| Genetic Sample ⁹ | | | X | | | | | | | | | | | | | | | | | |
| AE/SAE Review | SAEs collected from signing of informed consent form; AEs collected continuously from time of first dose. | | | | | | | | | | | | | | | | | | | |
| Concomitant medication review | Monitored from screening until the end of the final treatment period. | | | | | | | | | | | | | | | | | | | |

Footnotes:

1. All post dose time points are in reference to the first injection of IMP.
2. Assessments at these visits should be on the scheduled day however can be at any time in the day.
3. Early withdrawal assessments will be the same as Follow-Up.
4. ECG in triplicate at screening and single at all other time points.
5. ECG to be performed 6 hours post dose.
6. Vital Signs to be taken every 30 minutes from first IMP injection until completion of 2hr post dose monitoring period.
7. IMP administration consists of 3 syringes, all 3 syringes are to be administered as closely together as possible (preferably within 10 minutes).
8. Post dose Local tolerability at injection sites to be reviewed at 2, 6, 12, and 24 hours post dose.

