2. Assessments at these visits should be on the scheduled day however can be at any time in the day.
3. Early withdrawal assessments will be the same as Follow-Up.
4. ECG in triplicate at screening and single at all other time points.
5. ECG to be performed 6 hours post dose.
6. Vital Signs to be taken every 30 minutes from first IMP injection until completion of 2hr post dose monitoring period.
7. IMP administration consists of 3 syringes, all 3 syringes are to be administered as closely together as possible (preferably within 10 minutes).
8. Post dose Local tolerability at injection sites to be reviewed at 2, 6, 12, and 24 hours post dose.
9. The genetic sample is optional and can be taken any time after consent has been signed and the participant is randomized.

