15.3. Appendix 3: Assessment Windows

15.3.1. Definitions of Assessment Windows for Analyses

No assessment windows will be defined for analyses. Summaries and analyses will be based on nominal visits.

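### The SAP's baseline fallback counts untimed Day 1 readings as pre-dose, so an untimed post-dose ECG or vital-sign record could become baseline (a minor, latent rule error)

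*SAP*

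**What the plan says.** SAP 5.3 opens with the general rule: "The baseline value (in both Parts A and B) will be the latest pre-dose assessment with a non-missing value, including those from unscheduled visits". The second bullet adds the fallback: "If time is not collected, Day 1 assessments are assumed to be taken prior to dosing and used as baseline". The third deals with repeats: "Replicate assessments at a timepoint will be averaged, and the mean value will be used". None of the three mentions the planned time point.

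The schedules of activities place post-dose readings on Day 1 in both parts:
- **Part A vital signs** (Protocol 2.1): "Vital Signs to be taken every 30 minutes from start of infusion until completion of 2hr post dose monitoring period", with further marks at 6 h and 12 h.
- **Part A ECG** (Protocol 2.1): the grid marks pre-dose and 6 h.
- **Part B vital signs** (SAP 15.2.2): "Vital Signs to be taken every 30 minutes from first IMP injection until completion of 2hr post dose monitoring period".
- **Part B ECG** (Protocol 2.2): "ECG to be performed 6 hours post dose".

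Three other provisions bear on the point. SAP 15.5.2 uses planned time relative to dosing for summaries and derived parameters, unless otherwise stated. SAP 15.3.1 says: "Summaries and analyses will be based on nominal visits". SAP 15.4.1 classifies assessments as pre-treatment or treatment-emergent by date and time.

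**The concern.** The fallback suits a study in which everything on Day 1 happens before dosing. Here most of the scheduled Day 1 vital signs and one Day 1 ECG come after it. Because baseline is the latest eligible reading, a post-dose record admitted by the fallback can displace the true pre-dose one.

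ECG and vital signs are primary safety endpoints. Their baseline feeds the tables of maximum QTc relative to baseline (2.15 and 2.32), change in ECG values (2.16 and 2.33) and change in vital signs (2.17 and 2.34), and the QTc increase flag in SAP 15.8.2. No hypothesis is tested, so these descriptive displays carry much of the ECG and vital-sign evidence. The absolute flags in SAP 15.8.2 and 15.8.3 do not use baseline and are unaffected.

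**Working it through.** The plan attaches no figure to this rule, so there is none to reproduce. The check has four steps: count the readings that the wording could reach, remove those protected elsewhere, ask whether other provisions override the bullet, and show the arithmetic consequence.

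**1. Scheduled Day 1 readings, from the schedules of activities.** Protocol 7.1 gives a 2 h infusion and a further 2 h of monitoring, so half-hourly Part A readings run to 4 h: 4 / 0.5 = 8. Adding 6 h and 12 h gives 10. In Part B they run to 2 h: 2 / 0.5 = 4. The 24 h column sits under the Part A Day 1 heading. By the study-day formula in SAP 15.6.1 it normally falls on Study Day 2, so it is left out.

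| Assessment | Part | Pre-dose | Post-dose |
|---|---|---|---|
| ECG | A | 1 | 1 (6 h) |
| ECG | B | 1 | 1 (6 h) |
| Vital signs | A | 1 | 10 |
| Vital signs | B | 1 | 4 |

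**2. What is protected.**
- Protocol section 9 requires the actual date and time of every blood sample. The fallback therefore does not reach PK, sLAG3, LAG3+, haematology or chemistry as planned.
- Local tolerability has Day 1 post-dose reviews ("Post dose Local tolerability at injection sites to be reviewed at 2, 6, 12, and 24 hours post dose" in Part B), but no change-from-baseline display is planned for it.
- Part A urinalysis has only a 24 h sample under the Day 1 heading, normally Study Day 2.
- ECG and vital signs remain. No section requires a clock time for either.

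**3. Whether other provisions override the bullet.**
- SAP 15.5.2 gives way where something else is stated, and 5.3 can be read as stating something else.
- A visit label of Day 1, the unit named in 15.3.1, does not separate pre-dose from 6 h.
- SAP 15.4.1 works on date and time, which an untimed record lacks.
- SAP 5.3 admits unscheduled readings. Protocol 8.2.4 calls for two further ECGs after a prolonged QTc. If those repeats had neither a clock time nor a planned time point, the fallback could reach them too.

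**4. Consequence for one participant (QTc values assumed).**
- Pre-dose 385 msec, 6 h 448 msec: true rise 448 − 385 = 63, above the 60 msec flag, while 448 is below the absolute flag at 450. With 448 as baseline the rise is not computed and neither flag fires.
- A sustained rise of 65 msec is reported as 65 − 65 = 0. If the pre-dose and 6 h readings were instead averaged as replicates, baseline would move up by 65 / 2 = 32.5 and the reported rise would be 65 − 32.5 = 32.5. Both are below 60.
- If the 63 msec rise resolves, a later reading of 385 is reported as 385 − 448 = −63, a spurious fall.
- Group effect: if all participants share the same sustained change and one is reported as 0, the group mean shrinks by 1/6 = 16.7% in a Part A active stratum or 1/8 = 12.5% in a Part B active group.

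**The case against.** The best reply is that the error needs two things at once: no clock time, and a programmer who ignores a planned label such as 6 h. The first bullet of SAP 5.3 still asks for a pre-dose assessment. SAP 15.5.2 favours planned time and says that actual times will be shown in listings, which suggests that they are captured. The condition may also refer only to forms with no time field, not to an isolated missing time. Whether the ECG and vital-sign forms have that field cannot be seen from the documents.

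Most of this stands. It makes the error unlikely and confines it to ECG and vital signs. It does not remove it, because none of these provisions clearly overrides the bullet. The narrower reading is not wholly reassuring either: if a form had no time field, the fallback would apply to every participant's Day 1 records for that assessment.

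A reader might infer more than the documents support:
- **That any Day 1 assessment is exposed, including percent change in LAG3+ cells.** The recorded blood-sample times rule this out as planned.
- **That QTc safety review during the study would be weakened.** The criteria in Protocol 8.2.4 operate on live readings, and nothing ties them to the SAP derivation. Only later reporting is at stake.
- **That an effect would be understated at every later visit.** This holds for a sustained change only. A transient one produces a spurious fall instead.

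**Conclusion.** The concern holds as a latent, minor error in a stated rule. As written, SAP 5.3 allows an ECG or vital-sign record with no clock time and a post-dose planned time point to become baseline. If it did, change from baseline for that participant would be wrong at all visits in the tables named above, and a QTc rise above 60 msec could go unflagged. With 6 or 8 active participants per group, one such case is about 17% or 12.5% of the group.

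This assumes that a clock time is absent and that the bullet is applied literally over the planned label. The documents show neither happening and give no basis for a frequency. The QTc values are illustrations. Nothing here demonstrates bias, and no sample-size figure changes.

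**What to change.** Reword the second bullet of SAP 5.3 along these lines: *where no clock time is available, a Day 1 record is treated as pre-dose only if its planned time point is pre-dose; a record with a post-dose planned time point is never eligible as baseline.* An untimed unscheduled record with no planned time point is then ineligible too, and the scheduled pre-dose reading is kept. This agrees with SAP 15.5.2 and 15.3.1.

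The cost is one sentence and one condition in the baseline derivation. The schedule, data collection and sample size do not change. Making the edit before unblinding avoids having to choose a baseline after the data are seen.
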